16.7. SAE & AEs Requiring Discontinuation of Study Drug, including Pregnancies

ANY SAE, WHICH OCCURS AFTER A PATIENT HAS ENTERED THE STUDY, WHETHER OR NOT RELATED TO STUDY PRODUCT, MUST BE REPORTED TO THE SPONSOR OR ITS DESIGNEE IMMEDIATELY (WITHIN 24 HOURS) VIA TELEPHONE, EMAIL OR FACSIMILE. IF INITIALLY REPORTED VIA TELEPHONE, THIS MUST BE FOLLOWED-UP BY A FACSIMILE OR EMAIL OF THE WRITTEN SAE REPORT WITHIN 24 HOURS OF THE CALL TO THE SPONSOR OR ITS DESIGNEE.

Non-serious events that require discontinuation of study product (including laboratory abnormalities) should be reported to the Sponsor or its designee immediately and within 1 working day.

Patients who discontinue due to experiencing study product-related adverse events should be followed clinically until their health has returned to baseline status, or until all parameters have returned to normal. It is expected that the investigator will provide or arrange appropriate supportive care for the patient.

A patient who experiences a severe adverse event related to study product will be discontinued from the study. Please see SAE and Pregnancy Form Report Instructions for safety reporting instructions.

16.8. Pregnancy

At the time, Principal Investigator or site personnel becomes aware that a study patient became pregnant following study participation, the Principal Investigator or designee will report the pregnancy immediately by phone and/or by faxing a completed Pregnancy Report to the Sponsor or its designee within one working day of being notified of the pregnancy report.

The report will include the following elements:

- Patient (mother's) coded study identifier;
- Date of patient's last menstrual period;
- Total accumulated dose of study treatment administered to date;
- Date of study product administration.

The investigator will follow the patient until completion of the pregnancy and must assess the outcome in the shortest possible time but not more than 30 days within completion of the pregnancy.

Upon delivery, miscarriage or abortion, the Principal Investigator or designee must forward a follow-up Pregnancy Report with any relevant information on the present condition of the fetus to the Sponsor or its designee, including:

- Mother's coded study identifier(s);
- Gestational age at delivery, miscarriage or abortion;
- Birth weight, gender, length and head circumference, if available;
- Apgar scores recorded after birth, if available;
- Any abnormalities.

If the outcome of the pregnancy meets the criteria for immediate classification of an SAE (e.g., spontaneous or therapeutic abortion [any congenital anomaly detected in an aborted fetus is to be documented], stillbirth, neonatal death, or congenital anomaly), the investigator will report the event by phone and by faxing a completed SAE report form to the Sponsor or its designee within one working day of being notified of the pregnancy report.

If the trial is completed before the outcome of the pregnancy is known, the Sponsor or its designee will assume the responsibility for following up on the pregnancy. The Sponsor or its designee will contact the Investigator or Study coordinator on or around the potential expected date of delivery to follow-up on the outcome of pregnancy and will also check on the status of the infant 8 weeks post-delivery. Upon awareness of the pregnancy outcome and known status of the infant following 8 weeks of delivery, the investigator will complete the applicable pregnancy report forms and fax to the Sponsor or its designee within 1 day of being notified.

16.9. Post Study Adverse Events

16.9.1. Non-serious Adverse Events

Adverse events that are identified at the last assessment visit (or the Early Termination Visit) must be recorded on the AE eCRF with the status of the AE noted.

16.9.2. Serious Adverse Events

Serious adverse events that are identified on the last assessment visit (or the Early Termination Visit) must be recorded on the AE eCRF page and reported to Sol-Gel according to the procedures outlined above. Patients with unresolved previously reported serious adverse events, or any new serious adverse events identified on the last assessment visit, should be followed by the investigator until the events are resolved, or the patient is lost to follow-up. Resolution means the patient has returned to the baseline state of health, or the investigator does not expect any further improvement or worsening of the adverse event. The investigator should continue to report any significant follow-up information to Sol-Gel up to the point that the event has resolved. Any serious adverse event reported by the patient to the investigator that occurs after the last assessment and are determined by the investigator to be reasonably associated with the use of the study product, should be reported to Sol-Gel.

17. STUDY PRODUCTS / CLINICAL SUPPLIES

17.1. Method of Treatment Assignment

All eligible patients who complete the treatment phase of Phase 3 Study SGT-54-01 or Study SGT-54-02 within the Week 12 window and without protocol violation of missing visits (i.e., missing more than one of Visits 3, 4 or 5) will be offered to continue to this open-label, long-term safety study for up to 40 weeks. New patients, who were not previously enrolled in Study SGT-54-01 or Study SGT-54-02 will be enrolled to this open-label, long-term safety study for up to 52 weeks. During the study, patients will attend monthly visits. At Baseline, Visit 2, after satisfying all the Entry Criteria or Inclusion/Exclusion Criteria and after approval of the investigator, the patient will be assigned study product by the IWRS. Study medication will be marked in four (4)-digit pump number XXXX. At every visit, a new pump will be supplied to the patient.

17.2. Formulation

Study Product name: Encapsulated Benzoyl Peroxide Cream, 5%

Sponsor name: S5G4T-1

Active ingredients: benzoyl peroxide

Inactive ingredients: see list below

The inactive ingredients include: silicon dioxide, cetrimonium chloride, polyquaternium-7, lactic acid, hydrochloric acid, polyoxyl 100 stearate, cetyl alcohol, cyclomethicone 5, glyceryl monostearate, citric acid anhydrous, sodium hydroxide, edetate disodium, glycerin, phenoxy ethanol and water.

17.3. Study Products Packaging and Labeling

The study medication intended to be used will be stored together. The pump will carry a yellow, two-part label with a perforation. The tear-off section of the label will be attached to the study product dispensing log at the time the study product is dispensed. The label has spaces to enter the patient's initials and date of assignment and shows:

- Protocol number
- Patient number
- Pump number
- Patient Initials
- Dispense Date
- Dispenser Initials
- Contains: one (1) pump of Encapsulated Benzoyl Peroxide (E-BPO) Cream, 5%, 55g.
- Directions for use: Apply as directed, for topical use only.
- Storage conditions "Store at Room Temperature 20 to 25°C (68 to 77°F). Excursions permitted between 15 to 30°C (59 to 86°F)."
- Keep container tightly closed.
- Do not freeze and do not refrigerate

- Keep out of reach of children
- Study product warning. “Caution: New Drug - Limited by Federal (or United States) Law to Investigational Use”
- Sponsor information

17.4. Preparation, Dispensing and Storage Instructions

The study product must be dispensed only to study patients and only at study sites specified on the form FDA 1572 by authorized personnel as required by applicable regulations and guidelines.

Study product will be dispensed according to Investigator Global Assessment at: Baseline, Weeks 4, 8, 12, 16, 20, 24, 28, 32 and 36 for patients entering from study SGT-54-01 or study SGT-54-02 and for new patients at: Baseline, Weeks 4, 8, 12, 16, 20, 24, 28, 32, 36, 40, 44 and 48. Study product will be returned at: Weeks 4, 8, 12, 16, 20, 24, 28, 32, 36 and 40 for patients entering from study SGT-54-01 or study SGT-54-02 and for new patients at: Weeks 4, 8, 12, 16, 20, 24, 28, 32, 36, 40, 44, 48 and 52. Study product weight will be documented) prior to dispensing and after return of each pump per flow chart ([Section 13.9](#) and [Section 13.10](#)).

Each Patient will be instructed on the importance of returning his or her study product at each designated visit. If a Patient does not return his or her study product, he or she will be instructed to return it at the next visit.

The study coordinator will question the patient on history of study product use since the last visit and will record any missed doses (as recorded on the patient diary) in both the source documents and the appropriate eCRF. A patient who deviates significantly from the prescribed dosage will be counseled.

Study product should be stored at room temperature 20 to 25°C (68 to 77°F). Excursions permitted between 15 to 30°C (59 to 86°F). Do not freeze or refrigerate the product.

17.5. Dosing Instructions

Topical application of study product will be made to the face once daily at approximately the same time of the day, for the study period. Study product will be applied as a thin coating that is gently rubbed in to the skin.

Each patient will receive both verbal and written instructions (see [Appendix 1](#)) as to the proper dosing and study product application techniques.

Patients will be instructed to apply the study product, once a day after cleansing. No time interval between dosing and meals or any other activity is specified.

Patients will cleanse their face with the sponsor provided or approved cleanser using only the hands and pat dry with a soft clean towel. Patients will use a “pea-size” amount for each area of the face (chin, left cheek, right cheek, nose, left forehead and right forehead). The patient should apply the study cream on each area of the face as evenly as possible and gently rub the cream into the skin. Each pea-size amount should be used to evenly cover the following parts on the patient’s face: chin, left cheek, right cheek, nose, left forehead and right forehead excluding the mouth, eyes and lips. The patient should wash his/her hands after application but should not wash face at least 2 hours after study product application. Patients should wait at least 30 minutes before applying moisturizer/sunscreen after application of study product to the face. During the trial that investigators remind patients to avoid exposure to sunlight and sunlamps and to wear sunscreen when sun exposure cannot be avoided.

The patients will be instructed to continue using the same provided or approved facial cleanser and not to change products during the study. At each visit, patients are to be asked if they have changed their cleansing routine. The provided or approved cleanser and moisturizer/sunscreen should be applied according to the directions on the pump. Facial makeup (non-medicated) may be applied according to the patient’s normal daily routine (but not prior to 30 minutes after study product application); however, patients should be instructed not to apply the moisturizer or sunscreen or combination of them or wear make-up during study visits as it may interfere with the evaluator’s assessments. No other products should be used on the face.

The patient will be provided a set of instructions ([Appendix 1](#)) that includes study reminders and restrictions as described in this protocol. Patients will be instructed to bring the study product to each visit and to not apply study product one hour prior to the study visit. Patients should be instructed to store the study product at room temperature, not in the refrigerator or freezer and informed that the test article may bleach colored fabric.

17.6. Study Product Accountability and Study Records at Sites

Upon receipt of the clinical supplies, the study staff will conduct a complete inventory of study products and assume responsibility for their storage and dispensing. In accordance with federal regulations, the Investigators must agree to keep all study products in a secure, temperature-controlled location with restricted access.

All supplies sent to the Investigators will be accounted for and in no case used in any unauthorized manner. All used and unused study product will be appropriately inventoried by the clinical site and verified by the clinical monitor.

Study product will be weighed before dispensing and upon return and weights will be recorded on the appropriate source document and eCRF.

17.7. Return and Destruction of Study Product Supplies

Upon completion or termination of the study, all remaining pumps must be appropriately inventoried and returned to Sponsor or designee by a traceable method. All missing pumps of study products must be explained on the completed Clinical Supplies Return Form. The study site must keep a copy of the Clinical Supplies Return Form in the study file.

17.8. Additional Supplies Provided by Sponsor

- Regulatory study file system (Investigator Binder)
- Cleanser

- Moisturizer/sunscreen

18. STATISTICAL CONSIDERATIONS

18.1. General Statistical Methodology

All statistical processing will be performed using SAS[®] version 9.3 or later unless otherwise stated. Data will be summarized using descriptive statistics. No inferential testing or imputations for missing data will be performed. No interim analyses are planned for the co-primary variables.

For categorical parameters, the number and percentage of patients in each category will be presented. For continuous parameters, descriptive statistics will include n (number of patients), mean, standard deviation, median, minimum and maximum.

18.2. Populations Analyzed

All analyses will be performed using the Safety Population of the study. Part of this population will be referred as the extension safety population, and part as a new enrolled safety population. All patients who receive at least one confirmed dose of S5G4T-1 (in either Study SGT-54-01 or Study SGT-54-02, and in this study or for new patients in this study) and have at least one assessment will be included in the Safety Population.

The number of patients included in the Safety Population will be summarized.

18.3. Analysis of Efficacy

This study is not intended to assess efficacy, but rather the IGA is included to determine the need for treatment and subsequent re-treatment after treatment course (in either Study SGT-54-01 or Study SGT-54-02 or for new patients not previously enrolled in Study SGT-54-01 or Study SGT-54-02) and any subsequent 4-week courses, if applicable. Certain efficacy data and endpoints will, however, be summarized.

Descriptive statistics will be used to summarize the assessment of efficacy. IGA scores will be summarized at Baseline Visit of Study SGT-54-01 or Study SGT-54-02 or at the Screening visit of SGT-54-07 for those patients not previously enrolled in Study SGT-54-01 or Study SGT-54-02, and entry into the study (SGT-54-07) and every 4 weeks through end of the study. The number and percentage of patients who achieve treatment success at the scheduled study visits will be tabulated.

The number of retreatments is defined as the number of clinical confirmations of the condition for which the subject was initially treated after the first treatment period with S5G4T-1. For rollover subjects previously treated with Vehicle Cream, this is the number after the initial treatment in Study SGT-54-07. For rollover subjects previously treated with S5G4T-1, this is the number of treatments in Study SGT-54-07 following the cessation of the treatment which began in Study SGT-54-01 or Study SGT-54-02.

The number of treatment free days until the first retreatment (relapse) will be calculated and analyzed. For rollover subjects previously treated with Vehicle Cream, the number of treatment free days will be the number of days between the end of the initial treatment in study SGT-54-07 and the start of the next treatment in study SGT-54-07 if one should be needed or the end of the subject's participation in study SGT-54-07. For rollover subjects previously treated with S5G4T1, the number of treatment free days will be the of days between the end of the initial treatment that began in Study SGT-54-01 or Study SGT-54-02 and the start of the next treatment in study SGT-54-07 if one should be needed or the end of the subject's participation in the study SGT-54-07.

Descriptive statistics for retreatment rates will be presented. The time (number of days) to relapse will be analyzed using the Kaplan–Meier method. The median time to relapse will be calculated in addition to other appropriate descriptive statistics. Patients who discontinue study SGT-54-07 without relapse will considered censored in the Kaplan–Meier analysis.

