6. STUDY DESIGN

6.1 Overall Study Design

Approximately 700 patients will be enrolled at up to 56 sites. All patients in this open-label, long-term safety study will be assigned to treatment with S5G4T-1.

The objective of this study is to determine the long-term safety and tolerability of daily use of S5G4T-1 in papulopustular rosacea patients.

Patients who successfully completed the 12-week treatment period from Study SGT-54-01 or Study SGT-54-02 may be offered to continue in the long-term safety, open-label extension study (Study SGT-54-07) for up to an additional 40 weeks (sum of up to 52 weeks). The Sponsor may terminate the study once 300 patients complete a total of 28 weeks of treatment and 100 patients complete a total of 52 weeks.

Patients who completed the 12-week treatment period (± 4 days) for SGT-54-01 or SGT-54-02 and did not miss more than one visit (Visit 3, 4 or 5) in SGT-54-01 or SGT-54-02 will be admitted into the 54-07 study after the Entry Criteria have been met and an ICF has been signed. Qualified patients will receive study product at Baseline and will be treated for up to 40 weeks. At each visit, the patients will be assessed for a 5-point scale IGA of rosacea. If a patient is assessed as “clear” (0) or “almost clear” (1), the patient will not be dispensed the study product. If a patient is assessed as “mild”, “moderate” or “severe” (score of 2, 3 or 4, respectively), study product will be dispensed and the patient will use the study product daily according to patient instructions. Rosacea Quality of Life Questionnaire (RosaQoL) will be completed at Baseline, Visits 5, 8, 11, and 14 and at End of Study or at early termination. The RosaQoL data of patients who were enrolled from SGT-54-01 or SGT-54-02, will be used from the questionnaire completed at Visit 6/Week 12 of SGT-54-01 or SGT-54-02. Rosacea erythema severity and telangiectasia assessments will be completed at all study visits. At each visit, the following safety measures will be recorded: monitoring for any local and systemic AEs, cutaneous safety (dryness, and scaling) and local tolerability (itching and burning/stinging) assessments on a scale ranging from 0 (None) to 3 (Severe), vital signs and physical examinations.

A urine pregnancy test is required at all visits for all females of child-bearing potential.

Clinical Evaluations will be performed at:

1. Visit 1/Screening, only applies for new patients

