Descriptive statistics for time to relapse (number of treatment free days until retreatment) and number of retreatments will be presented. A confidence interval (CI) for the median time to relapse will be presented using the Kaplan–Meier method. Patients who discontinue in 54-07 while not being treated and had not yet previously relapsed will be considered censored in the Kaplan–Meier analysis.

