3 - Severe	xx (xx.x%)	xx (xx.x%)	xx (xx.x%)
Week 44^b			
n	xx	NA	xx
0 - None	xx (xx.x%)		xx (xx.x%)
1 - Mild	xx (xx.x%)		xx (xx.x%)
2 - Moderate	xx (xx.x%)		xx (xx.x%)
3 - Severe	xx (xx.x%)		xx (xx.x%)

^a Baseline is defined as the baseline value from SGT-54-01/SGT-54-02.

^b Table summaries based analysis visits, representing time from first dose of E-BPO 5% Cream.

SOURCE: USERNAME\SPONSOR\PROJECT\JOBNAME (DATE,TIME)

Table 14.2.4: Summary of Telangiectasia Assessment at Each Evaluation
(Safety Population)
(Page 5 of 5)

Telangiectasia Assessment	SGT-54-01/SGT-54-02 Vehicle Cream (N=xxx)	SGT-54-01/SG-54-02 E-BPO 5% Cream (N=xxx)	SGT-54-07 E-BPO 5% Cream (N=xxx)
Week 48 ^b			
n	xx	NA	xx
0 - None	xx (xx.x%)		xx (xx.x%)
1 - Mild	xx (xx.x%)		xx (xx.x%)
2 - Moderate	xx (xx.x%)		xx (xx.x%)
3 - Severe	xx (xx.x%)		xx (xx.x%)
Week 52 ^b			
n	xx	NA	xx
0 - None	xx (xx.x%)		xx (xx.x%)
1 - Mild	xx (xx.x%)		xx (xx.x%)
2 - Moderate	xx (xx.x%)		xx (xx.x%)
3 - Severe	xx (xx.x%)		xx (xx.x%)

^a Baseline is defined as the baseline value from SGT-54-01/SGT-54-02.

^b Table summaries based analysis visits, representing time from first dose of E-BPO 5% Cream.

SOURCE: USERNAME\SPONSOR\PROJECT\JOBNAME (DATE,TIME)

Table 14.2.5: Summary of Reoccurrence
(Safety Population)

	E-BPO 5% Cream (N=xxx)
Number of Retreatments	
n	xx
Mean	xx.x
SD	xx.xx
Median	xx.x
Min. to Max.	xx to xx
Number of Treatment Free Days Until First Retreatment	
n	xx
Median ^c (days)	xx.x
95% Confidence Interval ^c	(xx.x, xx.x)

^a Number of retreatments is defined as the number of times a subject's IGA goes from clear or almost clear to mild, moderate or severe after the subject was clear or almost clear while receiving E-BPO 5% Cream.

^b Number of treatment free days until first retreatment is defined as the number of days between an initial IGA assessment of clear or almost clear while the subject was receiving E-BPO 5% Cream until an IGA of mild, moderate or severe.

^c Median and 95% confidence intervals based on Kaplan-Meier method.

SOURCE: USERNAME\SPONSOR\PROJECT\JOBNAME (DATE,TIME)

Table 14.3.0.1: Summary of Extent of Exposure
(Safety Population)
(Page 1 of 2)

	SGT-54-01/SGT-54-02 Vehicle Cream (N=xxx)	SGT-54-01/SG-54-02 E-BPO 5% Cream (N=xxx)	SGT-54-07 E-BPO 5% Cream (N=xxx)
Total Number of Days of Exposure			
n	xx	xx	xx
Mean	xx.x	xx.x	xx.x
SD	xx.xx	xx.xx	xx.xx
Median	xx.x	xx.x	xx.x
Min. to Max.	xx to xx	xx to xx	xx to xx
Total Number of Applications			
n	xx	xx	xx
Mean	xx.x	xx.x	xx.x

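### Retreatment is summarised as a raw count per patient with no time at risk, so its mean depends on length of follow-up as well as on relapse risk

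*Protocol*

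**What the plan says.** Protocol section 18.3 first defines a count: "The number of retreatments is defined as the number of clinical confirmations of the condition". It then states: "Descriptive statistics for retreatment rates will be presented". It gives no numerator, denominator or time unit for the rate.

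SAP section 8.8.2 states: "Descriptive statistics for time to relapse (number of treatment free days until retreatment) and number of retreatments will be presented". Table 14.2.5 shows n, mean, SD, median and range of the count in one pooled column. Its footnote describes the count as "the number of times a subject's IGA goes from clear or almost clear to mild, moderate or severe", following clearance on product. It has no row for patient-time, for a rate or for the percentage of patients retreated.

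The other block of that table, "Number of Treatment Free Days Until First Retreatment", uses Kaplan-Meier. SAP section 8.8.2 says: "A confidence interval (CI) for the median time to relapse will be presented". It also gives a censoring rule: "Patients who discontinue in 54-07 while not being treated and had not yet previously relapsed will be considered censored". Both apply to the first relapse only.

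Three features bear on time at risk:

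- **Start of counting (SAP 8.8.2).** For patients previously on S5G4T-1, it starts when the treatment begun in the parent study ends. For patients previously on vehicle, it starts after their first S5G4T-1 course in SGT-54-07.
- **Dropout (Protocol 5.1).** Dropouts are not replaced.
- **Early stop (SAP 6.1).** "The Sponsor may terminate the study once 300 patients complete a total of 28 weeks of treatment" and 100 reach 52 weeks. Protocol 5.1 says these totals include the 12 parent-study weeks. Protocol 13.2 adds that, on an early stop, the sponsor will try to let patients finish six months of treatment.

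SAP section 10 explains only the removal of text about newly recruited patients.

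**The concern.** A retreatment count accumulates with time. A patient seen for 16 weeks has had fewer chances to relapse, clear and relapse again than one seen for 40. A mean of such counts over patients with different follow-up mixes relapse risk with length of observation, and the table gives the reader no way to separate them.

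The mixing does not need dropout. Suppose one patient on prior active treatment is clear at entry, and another on prior vehicle is not. The first can be at risk from Day 1, while the second must first clear on S5G4T-1 within the same 40 weeks. Both enter the one pooled column.

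The SAP recognises the issue elsewhere: its by-period adverse event tables use a separate denominator for each period. The retreatment count has no equivalent. At stake is whether the reported number of retreatments can be compared between the two prior-treatment groups, with another study, or with what would have been seen under a different stopping date.

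**Working it through.** There is no stated figure to reproduce: neither document gives a retreatment rate, a relapse probability or a dropout rate. The check asks how far the mean count moves when only follow-up changes.

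**Inputs from the documents.** Visits are every 4 weeks, SGT-54-07 lasts 40 weeks for rollover patients, and about 700 patients are planned. The stopping option requires 300 patients at 28 − 12 = 16 weeks in SGT-54-07 and 100 at 52 − 12 = 40 weeks.

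**A bound that needs no probabilities.** On scheduled visits alone, a patient clear at entry can relapse at most at Weeks 4, 12, 20, 28 and 36. The largest possible count is therefore 5 in 40 weeks and 2 in 16 weeks.

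**Assumed model.** Each patient is either off product (clear or almost clear) or on product. Per 4-week interval, the probability of relapse is r and of clearing is c. With p(k) the probability of being clear at the start of interval k + 1:

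p(k+1) = p(k)(1 − r) + (1 − p(k))c, and the expected count over K intervals is r × [p(0) + … + p(K−1)].

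With c = r = 0.3 and p(0) = 1, p(k) = 0.5 + 0.5 × 0.4^k, so the sum is K/2 + (1 − 0.4^K)/1.2:

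| Weeks in SGT-54-07 | K | Sum | Mean count (0.3 × sum) |
|---|---|---|---|
| 12 | 3 | 2.280 | 0.68 |
| 16 | 4 | 2.812 | 0.84 |
| 28 | 7 | 4.332 | 1.30 |
| 40 | 10 | 5.833 | 1.75 |

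**Mixed cohorts of 700 (the mixes are assumptions).** The second and third rows satisfy the stopping numbers exactly or with room to spare, and so do the last two.

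| Patients at each follow-up | Mean, all clear at entry | Mean, none clear at entry |
|---|---|---|
| 700 at 40 weeks | 1.75 | 1.25 |
| 300 / 200 / 200 at 40 / 28 / 16 | 1.36 | 0.87 |
| 100 / 200 / 400 at 40 / 28 / 16 | 1.10 | 0.61 |
| 100 / 200 / 400 at 40 / 16 / 12 | 0.88 | 0.40 |
| 100 / 600 at 40 / 28 | (175 + 780)/700 = 1.36 | not computed |

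The fourth row leaves 400 patients with 12 + 12 = 24 total weeks, slightly short of six months (about 26 weeks), so it is a low extreme. The third row meets six months if parent-study weeks count. The last row is for the case where they do not, with Week 28 as the first visit past six months.

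**Other settings, all clear at entry.** With c = 0.2 and r = 0.15, the full-follow-up mean is 1.04, against 0.51 to 0.81 in the three mixes with 16-week patients. With c = r = 0.5, it is 2.75 against 1.32 to 2.11.

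**Choice of denominator (c = r = 0.3, all clear at entry).**

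- Per total follow-up year: 0.84/(112/365.25) = 2.75 at 16 weeks, 2.42 at 28 weeks and 1.75/(280/365.25) = 2.28 at 40 weeks. This still drifts, because time on product is counted although a retreatment cannot start then.
- Per treatment-free year: 0.3/(28/365.25) = 3.91 at every follow-up length and in every mix computed. This constancy follows from the assumed constant relapse probability.

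**The case against.** The strongest reply is that nothing has been dropped. The protocol never defines the rate, and just before that sentence it defines a per-patient count. The SAP can be read as making loose wording specific, and SAP section 2 gives it precedence. A reader might infer that a defined output was promised and withdrawn; the documents do not support that. The gap remains on either ordinary meaning, however, because the SAP gives neither a rate per time nor a percentage retreated. Precedence settles which text governs, but does not make the count independent of follow-up.

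The second reply is that follow-up is already handled by Kaplan-Meier. For the first relapse this stands. A reader might expect the median to be inestimable whenever fewer than half of patients relapse. That is not right: under censoring, it is enough that the curve reaches 0.5. At relapse probabilities of 0.35, 0.25 and 0.15 per visit, the curve is at 0.65² = 0.42 by 8 weeks, 0.75³ = 0.42 by 12 weeks and 0.85⁵ = 0.44 by 20 weeks. Repeat retreatments are what remain uncovered.

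Two larger sizes are also tempting. One compares everyone at 16 weeks with everyone at 40, but the stopping option needs 100 patients at 52 total weeks, so an all-16-week cohort cannot arise at that point. The other takes 700 − 300 = 400 patients as having under 16 weeks. That is only an arithmetic ceiling: stopping is optional, and it ignores the six-month effort in Protocol 13.2.

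Finally, both documents say efficacy is not the study's purpose. Disposition, exposure and IGA listings are also reported, so it is speculative to say readers would mistake early exit for durable remission.

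**Conclusion.** The point holds for the retreatment count. Under one unchanged relapse process (c = r = 0.3, all clear at entry), full follow-up gives a mean 1.75/1.36 = 1.3 to 1.75/0.88 = 2.0 times that of the assumed early-stop mixes. The transition probabilities, the entry status and the mixes are all assumptions, because the documents supply none. The direction does not depend on them: a cumulative count cannot fall as follow-up lengthens.

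It is a worthwhile, inexpensive improvement to a secondary descriptive result. No safety conclusion changes, and the Kaplan-Meier analysis of first relapse can stand as planned.

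**What to change.** In SAP section 8.8.2 and Table 14.2.5, for patients who reached clear or almost clear on S5G4T-1, by prior treatment and overall:

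1. Add total retreatments divided by total treatment-free patient-time. Treatment-free time is time off product after a clear or almost clear IGA, until the next IGA of 2 or more or the end of participation. Give a 95% CI that allows for repeat events within a patient, for example by resampling patients or using a robust variance.
2. Add the Kaplan-Meier cumulative percentage with a first retreatment at 12 and 24 weeks after the end of first treatment, with 95% CI. A 36-week estimate is impractical for prior-vehicle patients: the first scheduled on-product IGA is at Week 4 of 40, which leaves at most 36 weeks apart from visit windows.
3. Keep the raw count as a supportive row, and state whether patients who never cleared are counted as zero or left out of n.
4. Record the change from rates to counts, and these additions, in SAP section 10.

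SAP section 8.1 already calls for presentation by parent-study assignment where applicable. The cost is a few table rows and one new derivation, treatment-free time after the first retreatment, which Table 14.2.5 does not now need. It uses IGA results and visit dates already collected.
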